8.5.2.3 Parameters Measured with SD-OCT

Parameters of High Resolution SD-OCT

A central reading center will perform quality control, analysis and interpretation of all SD-OCT data. The following parameters will be summarized:

- a. Ganglion Cell Layer (GCL) macular volume
- b. Retinal nerve fiber layer (RNFL) thickness
 - i. Average (360 degrees)
 - ii. Temporal quadrant
 - iii. Papillomacular bundle (PMB)
- c. ETDRS Macular Volume

SD-OCT parameters will be summarized at each follow-up visit (Years 2, 2.5, 3, 4 and 5), along with change from baseline to each follow-up visit. This summary will be repeated by comparing all-GS010 eyes to all-sham eyes.

The change of GCL volume and other parameters measured by SD-OCT (e.g., RNFL average thickness, RNFL Temporal Quadrant thickness, RNFL PMB thickness, ETDRS Macular Volume) from baseline to each follow-up visit (Years 2, 2.5, 2, 4 and 5) will be analyzed using a mixed-effects ANCOVA, including the subject as a random factor, the treatment and the baseline GCL volume (if available) as covariates in the model. The analysis will be performed using an alpha of 0.05 (two-sided test). The difference in the mean change from baseline (adjusted mean difference) to each follow-up visit between the two treatment groups (all-GS010 vs all-sham) and associated 95% confidence interval will be reported.

Additional Analyses and graphic presentations

A bar chart representation of GCL macular volumes at baseline will be produced (y axis: percentage; x axis: distribution of GCL macular volume values in mm^3). A bar chart of disease duration by GCL macular volume at baseline will be produced (y axis: percentage; x axis: 4 groups of GCL macular volume [≤ 0.5 ;]0.5;0.6];]0.6;0.7]; >0.7] combined with distribution of time from vision loss).

We will perform regression analyses of GCL macular volume at baseline in function of BCVA at baseline with calculation of R^2 and slope p value (using univariate Student test), and production of corresponding graphs. These analyses will be performed on all eyes, GS010 eyes and sham eyes.

LOESS model curves for GCL macular volume over time for all eyes, GS010 eyes and sham eyes, will be produced. Smoothing parameters selection will be based on the corrected Akaike's Information Criterion AICC (SAS default method with values from 0.3 to 0.6) and specified for each LOESS curve.

Subgroups analyses will be performed to investigate the relationship between OCT parameters and final BCVA at 5 years post treatment.

4 subgroups of eyes will be defined based on final LogMAR ranges:

- Group 1: ≤ 1 LogMAR
- Group 2: > 1 to ≤ 1.3 LogMAR
- Group 3: > 1.3 to ≤ 1.6 LogMAR
- Group 4: > 1.6 LogMAR

GCL macular volume absolute change from baseline by BCVA subgroups at 5 years post treatment will be provided. A corresponding bar chart will be produced (y axis: mean of GCL macular volume absolute change and x axis: subgroups of final BCVA).

A multivariate analysis on all eyes will be performed, in order to evaluate covariates impacting the final BCVA value, with the final LogMAR value as dependent variable. The covariates will be eye treatment status, GCL macular volume at baseline, GCL macular volume relative change from baseline (%) and LogMAR value at baseline. The same multivariate analysis will be performed for GS010 eyes and sham eyes separately.

We will perform regression analyses of GCL macular volume at final assessment in function of BCVA at final assessment with calculation of R^2 and slope p value (using univariate t-test from SAS proc mixed), and production of corresponding graphs. These analyses will be performed on all eyes, GS010 eyes and sham eyes.

We will perform regression analyses of BCVA at last assessment in function of GCL macular volume baseline value, with calculation of R^2 and slope p value (using univariate t-test from SAS proc mixed), and production of corresponding graphs. These analyses will be performed on all eyes, GS010 eyes and sham eyes.

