11.5.2.3 Parameters Measured with SD-OCT Including Ganglion Cell Layer Thickness/Volume and Topographical Map

The change of GCL thickness/volume and topographical map and other parameters measured by SD-OCT (e.g., retinal nerve fiber layer) from baseline to each follow-up visit will be based on mixed-effects ANCOVA, including the subject and the eyes of the subject as random factors, the treatment and the baseline GCL thickness/volume as covariates in the model. The analysis will be performed using an alpha of 0.05 (two-sided test). The difference in the mean change from baseline (adjusted mean difference) to each follow-up visit between the two treatment groups (all-GS010 vs all-sham) and associated 95% confidence interval will be reported.

The analysis will also be performed for the best-GS010 treated eyes compared to best-sham eyes; and worst-GS010 treated eyes compared to worst-sham eyes. The analysis will be similar to the FDA analysis of change of LogMAR from baseline to the follow-up visits.

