4.4 PREDETERMINED COVARIATES AND PROGNOSTIC FACTORS

GCL thickness/volume and topographical maps, best or worst-seeing eye (eye status) as determined prior to randomization and duration of vision loss at the time of treatment could be significant prognostic factors for the treatment effect.

The baseline LogMAR will also be used as a covariate for analysis of change in LogMAR. Similarly, the baseline of the endpoint being analyzed will be used as the model's covariate.

The investigative site will not be included in the analysis as the number of subjects recruited per site will be very small. However, stratification by geographical area may be performed as a sensitivity analysis. Neighboring countries can be pooled to reach at least 9 subjects per geographical entity. All analysis will be performed using an alpha of 0.05 (two-sided test).

These covariates will be used in the analyses presented in [Section 9.5 Efficacy Analysis](#).

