5.3 CHANGE FROM BASELINE

The change from baseline value is defined as the value at a given time point minus the baseline value.

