8.1 SUBJECT DISPOSITION

The number and percentage of subjects, who were enrolled and who completed the study will be presented, together with the number and percentage of subjects who withdrew from the study prematurely and a breakdown of the corresponding reasons for withdrawal. These data will also be listed according to the eCRF. The number and percentage of subjects in the Safety, mITT, PP, and Pediatric Populations will also be presented.

Number of subjects who missed visits and the subjects who attended a particular visit will be presented. In addition, number of missing data for visual acuity and important SD-OCT parameters will also be summarized.

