- The change of LogMAR BCVA from nadir to the visit of interest

Analysis for European Medicines Agency (EMA)

The primary analysis will be performed on the mITT Population. The change from baseline to each follow-up visit in the LogMAR acuity will be the response. The change from baseline of all-GS010 eyes will be compared to the change from baseline of all-sham eyes applying a mixed-effects ANCOVA model using the following terms (or covariate) in the model:

- Subject as a random factor.
- The baseline LogMAR as a covariate.
- Treatment as a fixed effect.

The null and alternative hypotheses for the EMA LogMAR analysis are:

$$H_0: \mu_{\text{All-GS010}} = \mu_{\text{All-Sham}}$$

$$H_1: \mu_{\text{All-GS010}} \neq \mu_{\text{All-Sham}},$$

where μ presents the mean change from baseline to the visit of interest in LogMAR and “All” represents all eyes treated with GS010 or Sham.

The investigative site will not be included in the analysis as the number of subjects recruited per site will be very small. However, stratification by geographical area may be performed as a sensitivity analysis. Neighboring countries can be pooled to reach at least 9 subjects per geographical entity. The analysis will be performed using an alpha of 0.05 (two-sided test).

An additional model may add the treatment by geographical interaction (geographical areas: USA and Europe) to investigate the generalizability of the treatment effect. The following model diagnostics may be checked: normality of error terms, independence of error terms, independence of the covariate and treatment effect, and homogeneity of error variances.

Analysis for Food and Drug Administration

The primary analysis will be based on the mITT Population. The change from baseline of the best-GS010 treated eyes will be compared to the change from baseline of the best-sham eyes (inter-subject comparison) using an ANCOVA with baseline LogMAR as covariate. The analysis will be performed using an alpha of 0.05 (two-sided test). The statistical significance in favor of the best-GS010 treated eyes against the best-sham eyes will show evidence of the advantage of using GS010 for halting visual acuity loss or improving visual acuity in subjects with LHON. The difference in the mean change from baseline (adjusted mean difference) between the two treatment groups and associated 95% confidence interval will be reported.

The null and alternative hypotheses for the FDA LogMAR analysis are:

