8.7 EXPLORATORY ANALYSES

8.7.1 Exploratory efficacy analyses

As an exploratory analysis, the response to treatment through Visit 5 (Year 5) using a MMRM model will be performed. The change from baseline in the LogMAR will be the response. Change from baseline of all-GS010 eyes will be compared to the change from baseline of all-sham eyes. The model will include subject as a random factor and fixed effects for treatment, follow-up visit (time point), eye status at baseline (better or worse), time from onset of disease and LogMAR at baseline as a covariate. The following interactions will be explored: baseline LogMAR and treatment; time from onset of disease and treatment; and eye status at baseline and treatment. The estimate of treatment effect at various follow-up time points and its 95% confidence interval (CI) will be presented. A UN@AR(1) (Autoregressive(1)) covariance structure will be fit to accommodate the doubly repeated measures data (repeated over time and eye). In the event of convergence problems with this covariance structure, other covariance structures will be explored.

Time course analysis of log of contrast sensitivity (LogCS), Humphrey visual field parameters and SD-OCT parameters will be conducted similarly to the time course analysis of LogMAR.

Other exploratory analyses will be performed for all analysed visits as a sensitivity analysis, excluding off-chart evaluations whose distance to the subject was superior to 2 meters. The endpoints analysed will be the ones described in 8.5.2.2 at eye level.

Additional exploratory analyses may be performed in the study.

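### The SD-OCT model in SAP 8.5.2.3 adjusts the RNFL and macular volume endpoints for baseline GCL volume but not for their own baseline, contrary to SAP 4.4

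*SAP*

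**What the plan says.** SAP 8.5.2.3 names GCL volume, three RNFL thicknesses (average, temporal quadrant, papillomacular bundle) and ETDRS macular volume. It analyses the change in each by a single mixed-effects ANCOVA at two-sided alpha 0.05, "including the subject as a random factor, the treatment and the baseline GCL volume (if available) as covariates in the model". No other baseline term is listed. The pattern comes from Protocol 11.5.2.3, which specifies "the treatment and the baseline GCL thickness/volume as covariates in the model".

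SAP 4.4 sets a general rule for the efficacy models: "the baseline of the endpoint being analyzed will be used" as the covariate. The EMA LogMAR model in SAP 8.5.2.2 follows it: "The baseline LogMAR as a covariate". SAP 4.4 also lists possible prognostic factors, among them "GCL thickness/volume and topographical maps, best or worst-seeing eye (eye status) as determined prior to randomization". GCL volume is therefore a legitimate candidate covariate. Nothing in 4.4 says that it replaces an endpoint's own baseline.

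On missing values, SAP 8.1 says that the "number of missing data for visual acuity and important SD-OCT parameters will also be summarized", which is a count and not a handling rule. SAP 6.2 applies LOCF to missing endpoints, not to a missing baseline covariate.

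**The concern.** A programmer who follows the term list in 8.5.2.3 fits a different model from one who follows 4.4, and the SAP gives no order of precedence. Under the literal list, four change scores are tested without adjustment for their own baseline. Part of any chance baseline difference between GS010 and sham eyes can then stay in the estimated effect, and precision may suffer.

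The availability qualifier on baseline GCL volume opens a second gap. An eye with valid RNFL or macular volume data but no baseline GCL value could be dropped, or could stay in a model without the covariate. The SAP does not say which. If either choice is left until results are visible, the pre-specification of these tests is weakened.

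**Working it through.** **Step 1: compare the sections.**

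| Endpoint (change) | Baseline term listed in 8.5.2.3 | Baseline term under 4.4 | Agree? |
|---|---|---|---|
| GCL volume | GCL volume | GCL volume | yes |
| RNFL average | GCL volume | RNFL average | no |
| RNFL temporal quadrant | GCL volume | RNFL temporal quadrant | no |
| RNFL papillomacular bundle | GCL volume | RNFL papillomacular bundle | no |
| ETDRS macular volume | GCL volume | ETDRS macular volume | no |

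One of five agrees and four do not. SAP 8.8 does not reconcile this: its GCL item removes GCL thickness and the topographical map, and no item concerns the SD-OCT covariate. SAP 8.7.1 says that time-course analysis of "SD-OCT parameters will be conducted similarly to the time course analysis of LogMAR", which by analogy implies own baseline, but that model is exploratory and does not settle the secondary ANCOVA.

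**Step 2: illustrate the size.** The plan states no correlations and no sample size, so every input here is assumed. Take standardised within-subject values with equal SDs. Let r be the correlation of own baseline with follow-up (0.7, 0.8, 0.9), q that of baseline GCL with own baseline (0.5, 0.7, 0.9), and s that of baseline GCL with follow-up. The residual variance of the change score is:

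- GCL only: 2(1−r) − (s−q)²
- own baseline only: 1 − r²
- both: 1 − (r² + s² − 2rsq)/(1−q²)

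The share of a chance own-baseline difference left in the effect with GCL only is (1−r) + q(s−q).

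*GCL informative only through own baseline (s = rq).* At r = 0.7, q = 0.5: s = 0.35; GCL only = 0.6 − 0.0225 = 0.5775; own only = 0.51; ratio 1.132; CI ratio √1.132 = 1.064; share left = 0.3 − 0.075 = 0.225. At r = q = 0.9: 0.1919/0.19 = 1.010; CI ratio 1.005; share left 0.019. Variance ratios, GCL only to own only:

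| | q = 0.5 | q = 0.7 | q = 0.9 |
|---|---|---|---|
| r = 0.7 | 1.132 | 1.090 | 1.034 |
| r = 0.8 | 1.083 | 1.057 | 1.021 |
| r = 0.9 | 1.039 | 1.027 | 1.010 |

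*GCL with some independent value (s = rq ± 0.1; 27 points including those above).*

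- GCL only to own only: 0.863 to 1.172, so the CI is from 7% narrower to 8% wider. GCL only wins when |s−q| > 1−r. That happens at 7 of the 27 points, with one tie.
- GCL only to both: 1.004 to 1.455, and at most 1.203 for q up to 0.7. The GCL-only model is nested in the joint model, so this ratio cannot fall below 1.
- Share left: −0.071 to 0.275.
- Reversal example (r = 0.9, q = 0.7, s = 0.53): 0.1711/0.19 = 0.901 against own only; 1.004 against both.
- Loss example (r = 0.7, q = 0.7, s = 0.59): 0.5879/0.51 = 1.153 against own only; 1.199 against both.

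*Cost of a second covariate*, (1 + 2/(n−4))/(1 + 1/(n−3)) with n subject pairs: 1.022 at n = 50 and 1.038 at n = 30 (both sizes assumed).

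*Simulation of the paired random-subject model* (50 pairs, between-eye ICC 0.5 and 0.8, 3,000 runs per setting). With s = rq, GCL only to own only was 1.01 to 1.16. The reversal example gave 0.89 against own only and 0.99 to 1.00 against both. The loss example gave 1.17 to 1.22 against both. When r is 0.9 between subjects but 0.7 within (q = 0.5 and 0.7), own-baseline adjustment itself leaves 14% to 16% of the imbalance, against 22% to 28% with GCL only.

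**Step 3: missing baseline GCL.** If a fraction m of subjects leaves the model, the CI widens by 1/√(1−m): 1.026, 1.054 and 1.118 for m = 0.05, 0.10 and 0.20 (assumed). Own baseline carries no such loss. By SAP 5.3, "The change from baseline value is defined as the value at a given time point minus the baseline value", so every eye with a change score already has its own baseline.

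**The case against.** The two sections can be read together: 4.4 supplies own baseline, 8.5.2.3 adds GCL, and 8.5.2.3 does not say that GCL is the only covariate. That reading is possible, but the SAP states it nowhere. An endpoint-specific list of terms would normally be programmed as written.

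The wording is inherited from the protocol. True, and it explains the list without reconciling it with 4.4.

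The magnitudes rest on no trial data, and the direction against own-only adjustment can reverse. Both points stand. The upper figure of 46% comes from one corner (r = q = 0.9, s = 0.91). There GCL only is 5% worse than own only, while own only is itself 38% worse than both, so most of that gap is not due to omitting own baseline. A straight swap of GCL for own baseline could therefore lose precision.

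Nothing suggests that baseline GCL is often missing, and SAP 5.2 takes the last non-missing pre-treatment OCT value, which limits the problem. This is fair: the 5% to 20% range is only illustrative. The missing rule is still a gap.

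Treatment was randomised between the two eyes, so no systematic bias arises, and these are secondary tests without multiplicity control. This stands too and limits the importance of the point.

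**Conclusion.** The concern holds. For four of five SD-OCT endpoints the listed model omits the own-baseline covariate that SAP 4.4 calls for, and the treatment of eyes without baseline GCL volume is undefined. The text comparison needs no assumptions.

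The effect on the results is modest and depends on unknown correlations. On the simplest assumption the CI is 0.5% to 6% wider than with own-baseline adjustment. Against GCL and own baseline together, the listed model never has lower residual variance, although at the low end the roughly 2% cost of the extra covariate cancels the gain. What is at stake is precision and residual chance imbalance in secondary efficacy results. The primary safety conclusion is untouched. The correction should be made because the ambiguity is real and removing it costs little.

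**What to change.** In SAP 8.5.2.3, state that each SD-OCT parameter is adjusted for its own baseline value. If GCL volume is kept as a prognostic factor for the RNFL and macular volume models, use it in addition to own baseline, never in its place, and replace the availability qualifier with an explicit rule.

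There are two workable forms. One uses own baseline alone in the main model, with GCL added in a labelled sensitivity model on the eyes that have it; this keeps every eye but gives up any independent information in GCL. The other puts both covariates in the main model with a stated rule that retains eyes lacking baseline GCL. Choose between them before SD-OCT treatment comparisons are examined further.

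Record the change from Protocol 11.5.2.3 in SAP 8.8. The edit is one phrase and one line and needs no new data. Keeping GCL as well costs one degree of freedom (about 2% of variance at 50 pairs, 4% at 30). The SAP is already at Final Version 2.0, and interim analyses were planned at Years 3 and 4, so any interim SD-OCT output from the listed model needs a short reconciling note.

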5. INTRODUCTION

5.1 Disease Review

Leber Hereditary Optic Neuropathy (LHON) is a rare, maternally inherited mitochondrial genetic disease, typically presenting as a non-syndromic optic neuropathy. Retinal ganglion cells (RGC), whose axons form the optic nerve, are the major cellular target affected by the resultant mitochondrial dysfunction. LHON was the first inherited human disease associated with point mutations in the mitochondrial DNA (mtDNA)¹ and it is considered the most common inherited genetic mitochondrial disorder.² LHON is a rare disease, and in Northern Europe, an estimated prevalence ranging from 1 in 30,000 to 1 in 50,000 has been reported.³⁻⁵

Three primary point mutations in the mtDNA are causative of LHON in approximately 90% of those affected. These point mutations, G3460A, G11778A and T14484C, occur respectively in the *ND1*, *ND4*, and *ND6* genes of the mtDNA, and all encode protein subunits of Complex I (CI) of the mitochondrial respiratory chain. The resultant dysfunction of CI and the respiratory chain lead to abnormal mitochondrial metabolic function, decreased adenosine triphosphate (ATP) production, and increased reactive oxygen species. This leads to cell death of the RGC and the resulting atrophy of the optic nerve.³

LHON manifests as acute to sub-acute, sequential, bilateral, painless vision loss. It is a bilateral disease, and the clinical manifestation is essentially predictive of bilateral involvement. Greater than 97% of patients are reported to have bilateral involvement at 12 months and occurrences of unilateral involvement in retrospective reports of cohorts with LHON are very rare.^{6,7} A G11778A *ND4* cohort was studied in which 53% reported bilateral involvement in ≤ 2 months, and 80% reported bilateral involvement in ≤ 6 months.⁸

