In the RESCUE/REVERSE studies, both eyes received standard antiseptic preparation, were administered topical local ocular anesthetic agents, and had pupillary dilation. Administration of an intraocular pressure-lowering agent preceded treatment. GS010 was administered once during the study via a single intravitreal (IVT) injection. Sham IVT injection was performed by applying pressure to the eye at the location of a typical procedure using the blunt end of a syringe without a needle. The right eye of each subject was randomly allocated to receive either GS010 or sham treatment in a 1:1 allocation ratio. The fellow (left) eye received the treatment not allocated to the right eye. Therefore, each subject received GS010 in one eye and sham treatment in the fellow eye.

The schema of the study design of the RESCUE/REVERSE studies is given below:

[figure not shown]

An algorithm with a testing hierarchy was employed to determine the best- and worst-seeing eye of each subject prior to randomization. The randomization was based on the right and left eye, because if the right eye was treated, the left eye would receive sham and vice versa, so the treatments were automatically balanced. However, the best- or worst-seeing eye at entry could have been a confounding factor, and it could not be excluded that the treatment effect would not be the same in the best and worst seeing-eye. In order to test this hypothesis with optimal power, an adaptive randomization technique called Efron's minimization¹⁰ method was used to minimize the imbalance of treatment groups between the best-seeing eyes and worst-seeing eyes.

Masking was accomplished with sham injection of the fellow eye. Thus, treatment allocation was double-masked for both the subject and the investigation (follow-up) team, except the physician and medical team that performed the GS010 administration and sham injection and the first follow-up visit. Centralized analysis of the Early Treatment Diabetic Retinopathy Study (ETDRS) visual acuity results, automated visual fields, SD-OCT, color vision and contrast sensitivity was performed by a masked central reading lab.

The schematic design of this long-term follow-up non-interventional study is given below:

Figure 1: Study Design Schematic of the Long-Term Follow-up of Subjects from the RESCUE and REVERSE Clinical Studies

Note: Inclusion into the long-term follow-up study will be allowed from Week 96 of the RESCUE/REVERSE studies up to 1 day prior to Year 2.5.

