8. STATISTICAL METHODS

All analyses will be performed on SAS Version 9.4 or higher.

Unless otherwise noted, categorical and binary variables will be summarized using counts and percentages. Percentages will be rounded to one decimal place.

Continuous variables will be summarized using the number of observations (n), mean, standard deviation (SD), median, first quartile (Q1), third quartile (Q3), minimum and maximum. Change from baseline or from nadir will also be summarized by a 95% confidence interval (CI).

Least square means, 95% CIs, and p-values will be reported from ANCOVA models. Estimated proportions with 95% CIs will be provided for Generalized Estimating Equation (GEE) models and for logistic regression models for responder endpoints. ANCOVA models will be run on all continuous endpoints, logistic regression for all subject responder endpoints, and GEE models for all eye responder endpoints.

Rounding rules are generally as follows:

- If the original variable has x decimal places, then minimum and maximum will be reported with x decimal places; mean, median, Q1, Q3, SD and CIs will be reported with x+1 decimal places.
- P-values will be reported with four decimal places.

Summary TFLs will display standard headers containing the sponsor name (“GenSight Biologics”) as well as a standard footer containing the name of the program used to generate the display, its path, and a date stamp. Headers, footers, titles, and column headers for tables will be repeated on every page of each display; pages will be numbered “Page x of y.” Visit labels in tables and figures will show visit name. Summary TFLs containing no applicable data will display a line reading, “No applicable data were reported” or similar wording. Dates and times will be presented using SAS DATE9. and SAS TIME5. formats.

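### The all-eyes slope test of baseline GCL volume on baseline BCVA ignores the pairing of eyes, and the other all-eyes models and mean-change intervals state no subject effect

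*SAP*

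**What the plan says.** **Baseline regression.** SAP 8.5.2.3, under its additional analyses and graphics, regresses baseline GCL macular volume on baseline BCVA. It reports R² and a "slope p value (using univariate Student test"). On the eye sets it says: "These analyses will be performed on all eyes, GS010 eyes and sham eyes".

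**Later regressions.** The same section regresses final GCL volume on final BCVA, and last BCVA on baseline GCL volume, on the same three eye sets. Each reports R² and a "slope p value (using univariate t-test from SAS proc mixed"). No RANDOM or REPEATED statement is given.

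**Multivariate model.** "A multivariate analysis on all eyes will be performed, in order to evaluate covariates impacting the final BCVA value". Its terms are listed: "The covariates will be eye treatment status, GCL macular volume at baseline, GCL macular volume relative change from baseline (%) and LogMAR value at baseline". No subject effect is among them.

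**Mean changes.** SAP 8 sets a general rule: "Change from baseline or from nadir will also be summarized by a 95% confidence interval (CI"). Changes averaged over all eyes appear in SAP 8.5.2.1 (LogCS from nadir), 8.5.2.2 (LogMAR from nadir) and 8.5.2.5 (visual field from baseline).

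**Design.** SAP 3.1 states that "each subject received GS010 in one eye and sham treatment in the fellow eye". Protocol 5.1 says of LHON: "It is a bilateral disease, and the clinical manifestation is essentially predictive of bilateral involvement".

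**Elsewhere the pairing is modelled.** The EMA LogMAR ANCOVA (SAP 8.5.2.2) and the SD-OCT treatment ANCOVA (8.5.2.3) have a random subject factor. All-eyes responder comparisons use GEE (8.5.2.4). The exploratory MMRM uses a covariance structure over time and eye (8.7.1).

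**The concern.** A Student test on a slope assumes independent errors. On the all-eyes set each subject enters twice, and in a bilateral disease the two eyes can be expected to resemble each other in both structure and acuity. The effective sample is then smaller than the number of eyes, the standard error is too small, and so is the p-value.

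The multivariate model, if fitted without a subject effect, errs in two directions. Covariates that vary mainly between subjects, such as baseline GCL volume and baseline LogMAR, get standard errors that are too small. Eye treatment status varies only within subject, so its standard error is too large.

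What is at stake is prognostic inference. SAP 4.4 names GCL measures as possible prognostic factors, the multivariate model is meant to find covariates that affect final acuity, and SAP 8.5.4 applies no multiplicity adjustment. An inflated slope test could be reported as a prognostic finding.

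**Working it through.** The documents state no sample size, effect or power for these regressions, so there is no planned figure to reproduce. The check measures the effect of ignoring the pairing.

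**Inputs from the documents:** two eyes per subject (SAP 3.1); two-sided alpha 0.05 (SAP 4.4).

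**Assumed inputs:** between-eye correlations ρx (predictor) and ρy (outcome), shown as a range because the documents give none; 30 and 60 subjects for the simulations.

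**1. Slope test on all eyes.** With m = 2 eyes per subject and no true association, the variance of the ordinary least-squares slope is inflated by about

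DE = 1 + (m − 1)·ρx·ρy = 1 + ρx·ρy,

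and the actual two-sided error is 2·[1 − Φ(1.96/√DE)].

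| ρx = ρy | DE | True SE / naive SE | Actual error |
|---|---|---|---|
| 0.3 | 1.09 | 1.04 | 0.061 |
| 0.5 | 1.25 | 1.12 | 0.080 |
| 0.7 | 1.49 | 1.22 | 0.108 |
| 0.9 | 1.81 | 1.35 | 0.145 |
| 1.0 (limit) | 2.00 | 1.41 | 0.166 |

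If either correlation is 0, DE = 1 and the error stays at 0.050.

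Null simulation (10,000 replicates, 30 and 60 subjects) agrees: 0.079 to 0.081 at 0.5, and 0.148 to 0.152 at 0.9.

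**2. One eye per subject.** The same simulation on a single eye per subject, as in the GS010-only and sham-only regressions, gave 0.048 to 0.054. Those need no correction.

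**3. Naive CI for an all-eyes mean.** The variance is understated by 1 + ρ, so coverage is 2·Φ(1.96/√(1 + ρ)) − 1.
- ρ = 0.5: 1.96/√1.5 = 1.60, coverage 89.0%.
- ρ = 0.7: 1.96/√1.7 = 1.50, coverage 86.7%.
- ρ = 0.9: 1.96/√1.9 = 1.42, coverage 84.5%.

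**4. Treatment term in the multivariate model.** Treatment contrasts the two eyes of one subject. Without a subject effect its SE is too large by about 1/√(1 − ρr), where ρr is the residual between-eye correlation after the covariates.
- ρr = 0.3: 1/√0.7 = 1.20.
- ρr = 0.5: 1/√0.5 = 1.41.
- ρr = 0.7: 1/√0.3 = 1.83.

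**5. After correction.** With a random subject intercept and 60 subjects, the simulated slope-test error was 0.048 (correlations 0.5) and 0.050 (correlations 0.8), from 500 replicates each with Monte Carlo SE about 0.01. With subject-clustered robust SEs it was 0.061 to 0.075 at 30 subjects and 0.056 to 0.065 at 60, over correlations of 0.3 to 0.9 in both variables.

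**The case against.** The strongest reply is that only one analysis names a test that assumes independence. For the two later regressions the SAP names PROC MIXED, which can carry a subject effect, and the multivariate model is silent. Since the SAP models the pairing in several other places, silence need not mean omission. This stands. A reader might infer that all the all-eyes regressions are shown to treat eyes as independent; the documents support that for the baseline regression only. For the others the defect is a missing specification. Naming PROC MIXED does not settle it, because without a RANDOM or REPEATED statement the procedure fits independent errors.

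A reader might also infer that the regressions' confidence intervals are wrong. SAP 8.5.2.3 plans R², slope p-values and graphs for them, and no interval. The interval point belongs to the all-eyes mean changes and depends on how those intervals are computed, which SAP 8 does not say.

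The sizes rest on assumed correlations, and the slope inflation needs correlation in both variables at once; at 0.3 it is slight. The 1.8-fold treatment SE is not a fixed value: it requires a residual correlation of 0.7, and the baseline and GCL covariates may absorb much of what the two eyes share. That model is also not the treatment comparison.

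Finally, the analyses are peripheral. SAP 8.8 lists the OCT regressions as additions to the protocol, the primary objective is safety, and no decision rule depends on these slopes. That limits the consequence but does not make the stated test valid.

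**Conclusion.** The point holds in a limited form. The all-eyes baseline slope test, followed as written, gives a p-value that is too small whenever GCL volume and BCVA are both positively correlated between eyes: an actual error of about 6% to 14.5% for assumed equal correlations of 0.3 to 0.9. The two PROC MIXED regressions and the multivariate model would share the fault unless a subject effect is added. The all-eyes mean-change intervals would under-cover if computed as though eyes were independent.

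It would be wrong to conclude that the trial's treatment comparisons are compromised. The all-eyes LogMAR and SD-OCT comparisons already include the subject, and the best-eye and worst-eye comparisons use one eye per subject. This is worth correcting before the prognostic results are interpreted, but it does not touch the primary safety analysis or the main efficacy results.

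**What to change.** Add to SAP 8.5.2.3 that every all-eyes regression and the all-eyes multivariate model includes a random subject intercept, and give the PROC MIXED statement. Subject-clustered robust SEs are an alternative, but they were somewhat liberal in the simulations at 30 subjects, so the random intercept is the safer default at these sizes.

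Add to SAP 8 that the 95% CI for any all-eyes mean change comes from the same kind of model. Label the pooled all-eyes R² as descriptive. Leave the GS010-only and sham-only regressions as they are.

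The cost is a sentence or two in the SAP and one extra statement per program; no new data are needed. The downside is that some slope p-values will become less favourable. In the multivariate model the treatment term would gain precision if the residual correlation is positive.
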